6.1. Data Collection

All data – including participant-reported and coordinator-facilitated data – will be collected on paper case report forms (CRFs) or electronic CRFs (eCRFs) that will be developed and maintained specifically for this project. Collected data will be entered into a secure database located at the CHI. Study staff at the CHI will be responsible for data collection and entry. All personnel involved in data collection and/or entry or data management will be appropriately trained by the trial coordinator.

6.2. Data Analysis

6.2.1. Analysis Plan

6.2.1.1. Participant-Reported Overall Health & Health Status

The primary outcome analysis of participant-reported overall health will be conducted using an area under the curve approach comparing the mean difference between arms in the EQ-VAS over the 21-day intervention period. Scores will range from 0-2100 (i.e., 0-100 for 21 days) for each participant.

Health status will be measured using the crosswalk value approach. Each level from each domain of the EQ-5D-5L is aggregated to form a number defining a unique health state, with 11111 (i.e., a “1” in all domains) representing the best possible health status and 55555 (i.e., a “5” in all domains) representing the worst possible health status. Raw values will be converted to an index value out of 1. Differences in mean index values will be compared between arms at various time points over the 12-week study period. Index values will be calculated using the United States crosswalk value set provided by the EuroQol group.^{65,66}

6.2.1.2. Symptom Severity & Duration

Symptom severity will be conducted using an area under the curve approach comparing the difference in total symptom scores over the 21-day intervention period between both arms. This gives a score range of 0-882 for each participant (i.e., 0-42 each day for 21 days). As a secondary analysis, we will compare the severity of each symptom individually using the same area under the curve approach. Scores for each symptom will range from 0-63 (i.e., 0-3 each day for 21 days). The incidence of severe symptoms (i.e., reporting a “3” for any symptom) will also be compared between arms throughout the intervention period.

The symptom duration analysis will compare the median time to symptom resolution from the start of the intervention period (or the first onset of symptoms if no symptoms were present at the start of the intervention period) up to the end of the intervention period (day 21) between both arms. Symptom resolution will be defined as a zero in all categories with no relapses.

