3.3. Inclusion/Exclusion Criteria

3.3.1. *Inclusion criteria:*

1. Adults (≥ 18) who test positive for SARS-CoV-2 by reverse transcriptase polymerase chain reaction (RT-PCR) in an outpatient setting
2. Access to internet

3.3.2. *Exclusion criteria*

1. Symptom onset greater than 7 days prior to enrolment
2. Supplementing regularly with >500 mg vitamin C, >1000 units vitamin D, >120 mcg vitamin K (any form), or >15 mg zinc taken daily within the past month
3. Currently taking warfarin or an equivalent vitamin K antagonist anticoagulant
4. End stage chronic kidney disease
5. History of calcium oxalate kidney stones
6. Active granulomatosis (sarcoidosis, tuberculosis, lymphoma)
7. Known hypercalcemia or hypervitaminosis D

8. Currently taking either of the following antibiotics: cephalexin, tetracyclines
9. Known allergy to any investigational product, silicon dioxide, cellulose, or medium chain triglyceride oil
10. Participating in an investigational study or participation in an investigational study within the past 30 days
11. Any reason which, under the discretion of the qualified investigator or delegate, would preclude the patient from participating.

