6.2.2. Statistical Methods

All analyses will follow an intention to treat approach. Continuous and quasi-continuous variables (participant-reported health & health status, primary & secondary severity analyses, and length of stay) will be compared between arms using unadjusted t-tests. Dichotomous outcomes (incidence of severe symptoms, delayed return to usual health, hospitalizations and deaths) will be compared between arms using Chi-square tests or Fisher's exact tests where appropriate. Time to symptom resolution will be displayed graphically with Kaplan-Meier curves and differences between arms will be compared with a log-rank test.

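### For participants symptom-free at the start, the symptom-duration clock begins at a post-randomisation onset, and those who never report symptoms have no defined time or event

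*Combined protocol and SAP*

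**What the plan says.** Section 6.2.1.2 (Symptom Severity & Duration) compares the median time to symptom resolution from the start of the intervention, "or the first onset of symptoms if no symptoms were present at the start of the intervention period", with observation running "up to the end of the intervention period (day 21) between both arms". The event is given as: "Symptom resolution will be defined as a zero in all categories with no relapses".

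Section 6.2.2 (Statistical Methods) gives the test: "Time to symptom resolution will be displayed graphically with Kaplan-Meier curves and differences between arms will be compared with a log-rank test". It also states: "All analyses will follow an intention to treat approach".

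Eligibility in section 3.3 is "Adults (≥ 18) who test positive for SARS-CoV-2 by reverse transcriptase polymerase chain reaction (RT-PCR) in an outpatient setting". The only criterion that concerns symptoms is the exclusion "Symptom onset greater than 7 days prior to enrolment", which does not exclude someone with no symptoms. Under section 3.7 and Table 1, the symptom questionnaire is completed on each of the 21 treatment days. Table 1 shows no symptom questionnaire at baseline.

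No section gives a time origin, an event or a censoring rule for a participant whose diary is zero throughout.

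**The concern.** The plan provides for participants without symptoms at the start. For them, two things depend on symptom onset during treatment: whether they have a survival time at all, and where it begins. If the supplements prevent or delay onset, the late-onset cases in the two arms are no longer comparable groups. A participant who never becomes ill, arguably the best result, adds nothing in favour of the arm that achieved it.

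The never-symptomatic also need a rule. Without one, they are either left out or handled by a choice made after the data are seen. The same gap touches anyone whose symptoms ended before the first dose: such a person has no symptoms at the start, and an onset that came before it.

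Total symptom duration is a listed secondary objective (section 2.1.2) and part of the hypothesis (section 2.2), so the estimate will be reported and interpreted.

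**Working it through.** The documents give no hazard ratio, event count or power for this outcome. The power statement in section 5 concerns the primary EQ-VAS outcome, so there is no planned figure to reproduce. The check therefore asks what the written rule does under stated assumptions.

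**Inputs from the plan.** 100 participants per arm (section 5), 1:1 allocation (section 4.5), observation to day 21 (section 6.2.1.2), log-rank test (section 6.2.2).

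**Assumptions, not in the documents.** A share f symptom-free at the start of 5%, 20% or 35%. Later onset in p = 50% of these on placebo and 25% on active. Onset uniform on days 2 to 10. Resolution rate 0.09 per day in those ill at the start, a median of ln 2 / 0.09 = 7.7 days (section 3.1 cites a median of 4 to 8 days from testing). Late-onset illness resolves either faster, at 0.22 per day (median 3.2 days), or at the same 0.09. Treatment has no effect on duration once a person is ill.

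**Step 1: who has a defined time.** Number per arm = 100 × [1 − f(1 − p)].
- f = 20%: placebo 100 × (1 − 0.20 × 0.50) = 90; active 100 × (1 − 0.20 × 0.75) = 85.
- f = 35%: 82.5 against 73.75.
- f = 5%: 97.5 against 96.25.

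A late-onset participant is observed for 21 minus the onset day, which is 19 to 11 days for onset on days 2 to 10.

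**Step 2: hazard ratio for resolution** (active over placebo; above 1 favours active). About 1,500 simulated trials per setting, with the never-symptomatic left out under the plan's rule.

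| f | Plan's rule, late illness shorter | Plan's rule, same duration | Symptomatic at start only | All randomised from day 1, late illness shorter |
|---|---|---|---|---|
| 5% | 0.98–0.99 | about 1.00 | about 1.00 | 1.01–1.02 |
| 20% | 0.96 | about 1.00 | about 1.00 | 1.06 |
| 35% | 0.93–0.94 | about 1.00 | about 1.00 | 1.11–1.12 |

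Rejection at the 5% level under the plan's rule stayed at about 5 to 7%. With onset equal in both arms, the plan's rule gives about 1.00.

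**Step 3: a second set of assumptions.** Log-normal duration with median 8 days, late illness treated like any other, later onset 60% on placebo and 30% on active. With f = 30%, the number without a defined time is 30 × 0.40 = 12 on placebo and 30 × 0.70 = 21 on active. The plan's rule gives about 0.99 to 1.00; counting everyone from the start gives about 1.16. With f = 15% the figures are about 1.00 and 1.08, and with f = 5% about 1.00 and 1.03.

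**Step 4: scale.** At f = 20% in Step 2, expected events are 2 × 80 × (1 − e^(−0.09 × 21)) = 136 among those ill at the start. The 10 + 5 late cases, followed for about 15 days, add 15 × (1 − e^(−0.22 × 15)) = 14. The standard error of the log hazard ratio is about 2/√150 = 0.16. A hazard ratio of 0.96 is a shift of ln 0.96 = −0.04, a quarter of one standard error.

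**The case against.** A reader might infer that the log-rank test as a whole does not compare the randomised groups. The documents do not support that. Everyone symptomatic at the start shares one origin, and the problem is confined to the rest. That subgroup may be small: recruitment follows recent positive tests, and section 4.3.4 presumes that a first symptom has occurred. However, section 4.3.4 relies on an inclusion criterion that section 3.3 does not contain, and section 6.2.1.2 itself provides for symptom-free starters, so the gap remains.

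A reader might also infer that the plan excludes the never-symptomatic, or that it biases the result against the active arm. The plan is silent on the first; the supportable word is undefined. The second needs late-onset illness to be shorter than other illness, which no section states. Without that assumption the hazard ratio is about 1.0.

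Three further objections stand. Censoring at day 21 is administrative, and shorter follow-up after late onset matters only if onset differs by arm. A preventive benefit is not lost to the trial, because the EQ-VAS and symptom-score areas under the curve and the incidence of severe symptoms need no onset. Finally, a clock from onset does measure illness duration in late cases, whereas starting everyone at day 1 measures something else: onset on day 10 with a two-day illness would count as about 12 days.

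None of these objections supplies the missing rule or makes late-onset cases comparable between arms when treatment affects onset.

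**Conclusion.** The concern holds for participants symptom-free at the start. Their entry and time zero depend on an event treatment may affect, which is inconsistent with the stated intention-to-treat approach, and the never-symptomatic have no defined time or event. If treatment changes onset, the comparison mixes non-comparable groups and does not count prevented illness.

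The numerical effect is modest and rests on assumptions. With onset of 50% against 25%, the hazard ratio falls below 1 only if late illness is shorter, reaching 0.93 to 0.94 at a symptom-free share of 35%, and is negligible at 5%. The more general loss is that prevention is invisible: about 1.00 under the plan's rule against about 1.16 counting everyone, in the 30% scenario. With equal onset there is no bias, and false positives are not materially increased. This is a secondary outcome, and the true symptom-free share is unknown. The rule should be settled before unblinding.

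**What to change.** Amend the SAP wording in section 6.2.1.2 as follows.

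1. **Main duration analysis:** all randomised participants with symptoms at the start, timed from the start of the intervention to sustained zero scores, with Kaplan-Meier curves and the log-rank test as planned. This restriction gave a hazard ratio of about 1.00 in every scenario above, as it should when treatment does not alter duration.
2. **New symptoms:** among those symptom-free at the start, compare the incidence of new symptoms by arm.
3. **Sensitivity analysis:** all randomised participants from day 1, with those at zero throughout counted as symptom-free from day 1. Label it time to sustained symptom-free status, not illness duration.
4. **Status at the start:** name the record that defines it. Table 1 has no baseline symptom questionnaire, so the day 1 form would serve, and the SAP should say whether it is completed before the first dose. State that people whose symptoms ended before the start belong to the symptom-free group.

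The planned diary suffices. The cost is slightly fewer participants in the main duration analysis: in the 20% scenario, expected events fall from about 150 to 136 and the standard error rises from about 0.16 to 2/√136 = 0.17.

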3.1. Study Design

This study is a double-blind, placebo-controlled, phase III randomized controlled trial powered to detect meaningful differences in the overall health and symptom severity of people with COVID-19 between the treatment and control arms. Eligible participants will be randomly assigned, using a web randomization system, in a ratio of 1:1 to one of the following groups: (1) nutrient therapy with vitamin D, vitamin C, vitamin K2, and zinc or (2) placebo. Total trial duration will be 12 weeks. Nutrients or placebo will be given for a period of 21 days following enrolment and randomization. The length of the intervention period (21 days) encompasses the most common period within which recovery occurs. The median duration of time to symptom resolution is 4-8 days from testing and yet a substantial number of people (26-47%) do not return to their usual state of health within 14-21 days.³³ Available guideline recommendations support a prolonged follow up period in order to assess patients experiencing ongoing symptomatic COVID-19 (signs and symptoms for 4-12 weeks) and those with post-COVID-19 syndrome (signs and symptoms >12 weeks).³⁴

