3.7. Outcome Measurements & Timeline

Participant-Reported Overall Health: measured using the EuroQol visual analogue scale (EQ-VAS).⁵⁹ The EQ-VAS records the respondent’s overall current health on a vertical scale between 0 and 100, where the end points are labelled “the best health you can imagine” (i.e., a score of 100) and “the worst health you

can imagine" (i.e., a score of 0). The EQ-VAS will be filled out each day while on the intervention (21 days total).

Health Status: Measured by combining one level from each of the five dimensions of the EuroQol 5-dimension 5-level (EQ-5D-5L) questionnaire⁵⁹ (mobility, self-care, usual activities, pain/discomfort, and anxiety/depression) to form a unique health state. Each dimension is divided into five levels of perceived problems: 1 – no problem, 2 – slight problems, 3 – moderate problems, 4 – severe problems, and 5 – unable to perform/extreme problems. The EQ-5D-5L questionnaire will be filled in at baseline (i.e., before starting the intervention) and weeks 1, 2, 3, 4, 8, and 12.

Symptom Severity & Duration: Measured using an internally-developed questionnaire specific for the most common COVID-19 symptoms, which include: fever, cough, shortness of breath, fatigue, headache, myalgia/arthralgia (body aches), nausea, vomiting, diarrhea, chills, altered taste, altered smell, and nasal congestion.^{11,60} Each symptom will be rated based on severity with a 4 point scale (0-3): 0-none, 1-slight, 2-moderate, and 3-severe. Participants will fill in this questionnaire each day while receiving treatment (i.e., for 21 days).

The questionnaire is largely based on recommendations from the US Food and Drug Administration (FDA) guidance document for investigators conducting community clinical trials for COVID-19 prevention or treatment.⁶¹ The symptoms were selected based on the most commonly reported COVID-19 symptoms in both the hospital and community setting.^{11,60} Some of the same symptoms are also included in the questionnaire being used in a study of vitamin C and zinc (COVIDAtz) at the Cleveland clinic, potentially allowing for comparison of results.²⁹

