Incidence of delayed return to usual health: Measured through follow-up calls with participants after the treatment period has ended. Participants will be contacted at weeks 4, 8, and 12 to assess this. The incidence of delayed return to usual health will be defined as the presence of any symptoms related to COVID-19 at the time of these calls as reported by the participant. Those experiencing prolonged COVID-19 symptoms lasting 4-12 weeks will be classified as experiencing "ongoing symptomatic COVID-19," while those still afflicted at 12 weeks will be classified as having "post-COVID-19-syndrome."⁶²

Hospitalization: the rate and type of hospitalization, as well as the length of stay, will be collected from participant medical records where possible and will otherwise be self-reported. Information will be collected throughout the 12-week study period.

All-Cause Mortality: date of death will be collected through medical records and obituary searches when medical records are not available. Information will be collected throughout the 12-week study period.

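### Symptom resolution requires zero on every diary item, with no stated allowance for symptoms present before COVID-19, so some recovered participants can never count as resolved

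*Combined protocol and SAP*

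**What the plan says.** Section 3.7 describes a daily questionnaire, completed for 21 days, covering "fever, cough, shortness of breath, fatigue, headache, myalgia/arthralgia (body aches), nausea, vomiting, diarrhea, chills, altered taste, altered smell, and nasal congestion". Each item is scored "0-none, 1-slight, 2-moderate, and 3-severe".

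Section 6.2.1.2 measures time from the start of intervention (or first onset, if later) "up to the end of the intervention period (day 21) between both arms", and adds: "Symptom resolution will be defined as a zero in all categories with no relapses". Section 6.2.2 compares arms with Kaplan-Meier curves and a log-rank test.

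Table 1 has medical history at baseline but no symptom score before day 1, and section 6.2.1.2 does not use the history. No exclusion criterion in section 3.3.2 names chronic cough, headache, pain or allergy. For the separate outcome of delayed return to usual health, section 3.7 does attribute symptoms, counting "the presence of any symptoms related to COVID-19 at the time of these calls as reported by the participant".

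**The concern.** Several diary items are common outside COVID-19. Two things follow from the stated rule.

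- **Steady symptoms.** A participant whose usual score on one item is 1 cannot reach zero in all categories, however complete the recovery from COVID-19. That person is censored at day 21 whatever the treatment did.
- **Sporadic symptoms.** Relapse is not defined. If any later non-zero score counts, the event date is the day after the last non-zero score. Someone recovered on day 5 with one unrelated slight headache on day 18 is then dated as resolved on day 19. The exposure is uneven: recovery on day 5 must hold for 17 diary days (days 5 to 21), recovery on day 21 for one.

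Symptom duration appears in the overarching goal (section 2.1) and the hypothesis (section 2.2) and is secondary objective 3. At stake are an overstated median and a treatment effect pulled toward the null.

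**Working it through.** **Number of items.** Section 3.7 lists 13 symptoms: 13 × 3 = 39 per day, and 39 × 21 = 819. Section 6.2.1.2 says: "This gives a score range of 0-882 for each participant (i.e., 0-42 each day for 21 days". That implies 42 / 3 = 14 items (14 × 3 × 21 = 882). The two sections disagree on how many items must be zero. The argument is the same with either count.

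**Steady symptoms, closed form.** If a share c always scores at least 1 on some item, the observed share resolved by day 21 is the true share × (1 − c). Section 3.1 says that "a substantial number of people (26-47%) do not return to their usual state of health within 14-21 days". Taking 53-74% as a rough proxy for true resolution:

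- c = 10%: 48-67%
- c = 15%: 45-63%
- c = 20%: 42-59%

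At the lower figure the median is not reached by day 21 once c exceeds 1 − 0.50/0.53 = 5.7%.

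**Sporadic symptoms, closed form.** For a person symptom-free on day 6, the chance that the 15 later diary days are all zero is (1 − p)^15, where p is the daily chance of an unrelated score: 93% at p = 0.5%, 86% at 1%, 63% at 3%, 46% at 5%.

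**Log-rank power by simulation.** The plan states no power for this outcome, so there is no figure to reproduce. From the documents: 100 per arm, 21 diary days, log-rank test, and a placebo median of 6 days (inside the 4-8 days in section 3.1, counted there from testing). Assumed: exponential recovery, recovery hazard ratio 1.5, two-sided 0.05, any later non-zero score counting as a relapse, and the background rates. The figures come from 3,000 to 10,000 simulated trials per row. The last column adds 20% of participants in both arms who do not recover from COVID-19 by day 21.

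| Unrelated symptoms | Power | Placebo median (days) | Power with 20% slow recoverers |
|---|---|---|---|
| None | 79% | 6.6 | 29% |
| 0.5% per day | 72% | 7.3 | 26% |
| 1% per day | 64% | 8.0 | 24% |
| 3% per day | 44% | 11.1 | 18% |
| 5% per day | 32% | 13.7 | 16% |
| 10% chronic | 47% | 7.6 | 22% |
| 15% chronic | 37% | 8.3 | 18% |
| 15% chronic and 5% per day | 18% | 15.8 | 11% |

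**Why the last column is needed.** Exponential recovery with median 6 leaves 2^(−14/6) = 20% unresolved at day 14 and 2^(−21/6) = 9% at day 21, below the 26-47% in section 3.1. Adding 20% slow recoverers gives 0.20 + 0.80 × 0.088 = 27% at day 21.

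**Effect of the fix.** If usual level is recalled accurately, scoring against it restores power at 15% chronic and no sporadic symptoms from 37% to about 80%. It does not help with sporadic symptoms while resolution must hold to day 21: at 5% per day power stays near 32%. A rule of three consecutive days gives 77-79% at 1-5% per day, but the simulation contains no true COVID-19 relapses, which that rule would count as recovered.

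**The case against.** A sustained, all-zero definition is a recognised strict choice, and section 3.7 calls the questionnaire specific to COVID-19 symptoms. The form is not in the documents, so an instruction to score only new or COVID-related symptoms cannot be ruled out. Altered taste and smell already imply change from usual, fever is measured by thermometer, and chills or vomiting are unlikely as steady scores. Relapse in ordinary use means return of the illness, so an unrelated headache need not be one. All of this narrows the exposure, but it leaves the stated rule without an allowance for the remaining items.

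Four stronger readings are tempting but not supported:

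- **That the diary ignores attribution.** The documents show only that the protocol states no attribution rule.
- **That the plan contradicts itself.** Symptom duration and delayed return to usual health are separate objectives (section 2.1.2, items 3 and 4) and may use different criteria.
- **That the comparison is biased.** Unrelated symptoms should balance under blinded randomisation. Gastrointestinal items, which section 7.2.1 treats as expected side effects of the product, are a different question.
- **That planned power is lost, or that the outcome mostly records everyday symptoms.** Section 5 powers only the primary outcome. At 0.5-1% per day the loss is modest, and with many slow recoverers power is low before any unrelated symptom is counted.

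**Conclusion.** The point holds as a definitional weakness in one secondary outcome. Under the stated rule, people with a steady pre-existing symptom cannot resolve. If every later non-zero score is a relapse, sporadic unrelated symptoms also delay the date. Both lengthen the reported median and dilute a true effect. The direction follows from the definition. The size does not: background rates, chronic share, hazard ratio and recovery distribution are all assumptions. Under them, power of about 80% falls to between 18% and 72%; with 20% slow recoverers it goes from about 30% to between 11% and 26%. The primary EQ-VAS analysis is unaffected.

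**What to change.** 1. At the existing baseline contact, record the usual pre-COVID score (0-3) for each diary item.
2. Define resolution as the first day from which every item is at or below its usual level, sustained to day 21. This also states what a relapse is.
3. Keep the all-zero, no-relapse version as a sensitivity analysis. Add the first of three consecutive days at or below usual level as a further one. It should not be the main definition, because it counts a person whose COVID-19 symptoms return as recovered. Comparing it with the main result shows how much sporadic symptoms matter, which step 2 does not address.
4. State in sections 3.7 and 6.2.1.2 whether participants are told to score only COVID-related symptoms.
5. Reconcile the 13 listed items with the 14 implied by the score range.

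The cost is one short form and a revised definition, fixed before unblinding. The drawback is that usual level is recalled during acute illness, so some values will be wrong.
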